## 6.4. Recurrence or occurrence of secondary malignancy and Survival Follow-Up

Follow-up for recurrence or occurrence of a secondary malignancy must be collected at each clinic visit as per protocol. All patients will be followed up (regardless of the duration of treatment) until the time for final analysis, every 16 weeks for the first 3 years from initiation of study treatment (also, at the end of treatment) and every 6 months thereafter for the remainder of follow-up period\*. If new anti tumor therapy is initiated for either recurrence or occurrence of a secondary malignancy at any time during this period, this and all other pertinent data obtained should be recorded on the appropriate CRFs. The final analysis of primary endpoint (DFS) will be performed when approximately 245 DFS events have been reached.

\* Patients who complete 3-year treatment will be followed up for DFS every 6 months from the date of CT or MRI at the end of study treatment.

Patients who withdraw from treatment before DFS events will be followed up for DFS every 16 weeks from the date of CT or MRI at the withdrawal. After 3 years from initiation of study treatment, CT or MRI for DFS will be performed every 6 months from the first scan date that is performed after more than 3 years from initiation of study treatment.

All patients will be followed up for OS status (regardless of the duration of treatment) approximately every 16 weeks from DFS events until the time for final DFS analysis. Survival status can be ascertained by telephone contact.

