## 8.2. Reporting Period

Serious adverse events require immediate notification to sponsor or its designated representative beginning from the time that the patient provides informed consent, which is obtained prior to the patient's participation in the clinical trial, ie, prior to undergoing any trial-related procedure and/or receiving investigational product, through and including 28 calendar days after the last administration of the investigational product. Any serious adverse event occurring any time after the reporting period must be promptly reported if a causal relationship to investigational product is suspected.

Non-serious adverse events should be recorded from the time the patient has taken at least one dose of trial treatment through last patient visit.

If a patient begins a new anticancer therapy, the adverse event reporting period for non-serious adverse events ends at the time the new treatment is started. Death must be reported if it occurs during the serious adverse event reporting period after the last dose of investigational product, irrespective of any intervening treatment.

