#### 8.5. Serious Adverse Events

A serious adverse event or serious adverse drug reaction is any untoward medical occurrence at any dose that:

- Results in death;
- Is life-threatening (immediate risk of death);
- Requires inpatient hospitalization or prolongation of existing hospitalization;
- Results in persistent or significant disability/incapacity;

• Results in congenital anomaly/birth defect.

Progression of the malignancy under trial (including signs and symptoms of progression) should not be reported as a serious adverse event unless the outcome is fatal during the trial or within the safety reporting period. Hospitalization due to signs and symptoms of disease progression should not be reported as serious adverse event. If the malignancy has a fatal outcome within the safety reporting period, then the event leading to death must be recorded as an adverse event and as a serious adverse event with CTCAE Grade 5 (See Section 8.7, Severity Assessment). Any histopathologically confirmed secondary malignancy must be reported as SAE.

Medical and scientific judgment should be exercised in determining whether an event is an important medical event. An important medical event may not be immediately life-threatening and/or result in death or hospitalization. However, if it is determined that the event may jeopardize the patient and/or may require intervention to prevent one of the other outcomes listed in the definition above, the important medical event should be reported as serious.

Examples of such events are intensive treatment in an emergency room or at home for allergic bronchospasm; blood dyscrasias or convulsions that do not result in hospitalization; or development of drug dependency or drug abuse.

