## 9.4.1. Analysis of Adverse Events

The serious adverse event reporting experience for this study begins from the time that the patient provides informed consent while the adverse event reporting experience for this study begins upon receiving the first dose of study drug and ends 28 days after the last dose of study drug is administered. All AEs (serious and non-serious) reported from the first day of study treatment up to 28 days post study treatment will be considered treatment emergent AEs (TEAEs).

Frequencies of patients experiencing at least one AE will be displayed by body system and preferred term according to MedDRA terminology. Detailed information collected for each AE will include: A description of the event, duration, whether the AE was serious, intensity,

relationship to study drug, action taken, and clinical outcome. Intensity (severity) of the AEs will be graded according to the CTCAE Version 4.0. Emphasis in the analysis will be placed on AEs classified as treatment emergent.

Summary tables will present the number of patients observed with TEAEs and corresponding percentages. Within each table, the AEs will be categorized by MedDRA body system and preferred term. Additional subcategories will be based on event intensity and relationship to study drug.

Individual patient listings will be prepared for all AE data.

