**7.5.1. Adverse Events**

Adverse event (AE) terms recorded on the CRF will be mapped to PT and SOC using the Medical Dictionary for Regulatory Activities (MedDRA). The severity of AEs will be evaluated by the investigator by employing the CTCAE v4.03 (Cancer Terminology Criteria for Adverse Events). The investigator will also judge each event to be “not related” or “related” to study treatment.

A TEAE is defined as any AE with an onset date on or after the date of the first dose of study treatment or any ongoing event on the date of the first dose of study treatment that worsens in severity after the date of the first dose of study treatment.

The AE observation period is defined as the time from date of the first dose of study treatment until 28 days after the last dose of study drug is administered. TEAEs with an onset date through the end of the study observation period will be summarized by treatment arms. The Grade 5 TEAEs with onset date outside of the observation period may be tabulated separately.

For summaries of subject incidence of TEAE, at each level of summarization, a subject will be counted only once for each AE preferred term experienced by the subject within that level (i.e., multiple episodes of events with the same preferred terms will be counted only once). Selected summaries of subject-incidence of AEs (as defined in Section 7.5.1.2) will include the risk difference (defined as the proportion with the event in the axitinib arm minus the proportion with the event in the placebo treatment arm) with 95% CIs and the risk ratio (or relative risk; defined as the proportion with the event in the axitinib group divided by the proportion with the event in the placebo group) with 95% CIs. An overall summary of treatment emergent adverse events (including those that stopped more than 28 days after the decision to discontinue study treatment) will be provided with the number and percent of subjects who experienced the following in each treatment group:

- Subjects with a TEAE
- Subjects with a Related TEAE
- Subjects with a Serious TEAE at any time (including active treatment period plus follow-up period)
- Subjects with a Serious Related TEAE
- Subjects with a Worst-Grade of  $\geq 3$  TEAE
- Subjects with a Worst-Grade of  $\geq 3$  Related TEAE
- Subjects with a Grade 5 TEAE at any time

---

|           |   |                 |           |
|-----------|---|-----------------|-----------|

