| Palmar-Plantar Erythrodysesthesia (PPE)     | MedDRA PTs: Palmar-plantar erythrodysesthesia syndrome, palmar erythema, and plantar erythema.  |
| Fatigue and Asthenic Conditions             | MedDRA PTs: Asthenia, Autonomic nervous system imbalance, Decreased activity, Listless, Sluggishness, Chronic fatigue syndrome, Fatigue and Malaise)  |
| Hepatic Disorders                           | Cholestasis and jaundice of hepatic origin (SMQ narrow)
Drug-related hepatic disorders - comprehensive search (SMQ narrow)
Liver related investigations, signs and symptoms (SMQ narrow)
Hepatic & Hepatobiliary disorders (HLGT)  |
| Congestive Heart Failure/Cardiomyopathy     | MedDRA PTs: Acute left ventricular failure, Acute right ventricular failure, Cardiac failure, Cardiac failure acute, Cardiac failure chronic, Cardiac failure congestive, Cardiac failure high output, Cardiogenic shock, Cardiopulmonary failure, Chronic left ventricular failure, Chronic right ventricular failure, Cor pulmonale, Cor pulmonale acute, Cor pulmonale chronic, Ejection fraction decreased, Left ventricular failure, Low cardiac output syndrome, Neonatal cardiac failure, Right ventricular failure, Ventricular failure, Cardiac output decreased, Cardio-respiratory distress, Central venous pressure increased, Diastolic dysfunction, Left ventricular dysfunction, Myocardial depression, Oedema due to cardiac disease, Right ventricular dysfunction, Systolic dysfunction, Ventricular dysfunction, Cardiomyopathy acute, Congestive cardiomyopathy, Ejection fraction abnormal, Ejection fraction decreased. |
| Carcinogenicity (Second Primary Malignancy) | SMQ malignant or unspecified tumours, SMQ Malignant tumours, SMQ Tumours of unspecified malignancy and the Lower Level Term (LLT): Secondary primary malignancy.  |

For Cardiovascular disorders: Include Cardiac disorders, Nervous system disorders, Vascular disorders

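### The second primary malignancy safety summary stops 28 days after the last dose and uses crude proportions, although these cancers are followed to the final analysis

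*SAP*

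**What the plan says.** SAP 7.5.1 runs the AE observation period from first dose "until 28 days after the last dose of study drug is administered", and "TEAEs with an onset date through the end of the study observation period will be summarized by treatment arms". SAP 7.5.1.2 lists special-interest TEAE categories, among them one labelled "Carcinogenicity (Second Primary Malignancy", and sets no longer window for it. SAP 7.5.1 gives these categories a risk difference and a risk ratio based on the proportion of subjects with the event. SAP 7.5.1.2 adds a Kaplan-Meier display only where there are at least 10 events per arm.

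Protocol 6.4 says "Follow-up for recurrence or occurrence of a secondary malignancy must be collected at each clinic visit as per protocol", and continues this to the final analysis whatever the duration of treatment. A secondary malignancy is also a DFS event (SAP 5.1), but SAP 7.1.1 describes no breakdown of DFS events by type.

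The end of the treatment-emergent period is stated in two ways. In SAP 7.5.1, "A TEAE is defined as any AE with an onset date on or after the date of the first dose of study treatment", with no end date. In protocol 9.4.1, all AEs "reported from the first day of study treatment up to 28 days post study treatment will be considered treatment emergent AEs".

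On serious events, protocol 8.5 says "Any histopathologically confirmed secondary malignancy must be reported as SAE". Protocol 8.2 requires SAE reports "through and including 28 calendar days after the last administration of the investigational product", and after that only where a causal link to the study drug is suspected.

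**The concern.** A window of last dose plus 28 days suits acute toxicity. A new cancer can appear late, and the sponsor both named it as a special interest and arranged to look for it until the end of the study. The planned summary does not use that later follow-up.

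The window also ends at a different time for each patient, because treatment is planned for 1 to 3 years and can stop earlier for toxicity or recurrence. A crude proportion has no person-time denominator. If one arm stops treatment sooner, its patients are counted over a shorter period and its proportion falls for that reason alone. The risk ratio then mixes any drug effect with relative treatment duration.

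**Working it through.** **Follow-up length, checked against the plan's own figure.** Inputs from SAP 3.3: accrual 24 months, study period 60 months, 23% dropout by 18 months, 700 patients, and the 2-year DFS rates in its Table 2 (placebo 70/35/33%, axitinib 79/61/51%, in 90/1/9% of patients). Hazards are -ln(rate)/24 per month for DFS and -ln(0.77)/18 for dropout. Simulating these gives 251 expected DFS events by month 60, against the planned 245. The inputs are therefore a fair picture of the follow-up the plan expects.

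**Share of one patient's follow-up outside the window.** For a patient with no DFS event or dropout, follow-up F is 36 to 60 months. With treatment t and 28 days = 0.92 month, the share left out is (F - t - 0.92)/F:

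- F = 48, t = 12: 35.1/48 = 73%
- F = 48, t = 24: 23.1/48 = 48%
- F = 48, t = 36: 11.1/48 = 23%
- Extremes: 78% (F = 60, t = 12) and 0% (F = 36, t = 36)

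**Share over the whole trial.** Protocol 7.1 ends scheduled tumour assessment at recurrence or secondary malignancy. With follow-up ending at a DFS event, the plan's dropout, and equal treatment in both arms, the share left out is 58% at 12 months of treatment, 44% at 18, 32% at 24 and 12% at 36. Without dropout it is 66%, 52%, 40% and 17%.

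**Effect on the risk ratio.** Assumptions not in the documents: 350 patients per arm, a second-primary rate of 1% per year on placebo, and exponential treatment times capped at 36 months. DFS and dropout follow the plan. Expected cases in the window are approximately 350 x rate x mean in-window years. Mean disease-free follow-up is 2.28 years (axitinib) and 2.05 years (placebo).

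| Median treatment, axitinib/placebo (months) | Mean in-window years | Captured | Ratio if true 1.0 | Ratio if true 1.5 |
|---|---|---|---|---|
| 12/24 | 1.00 / 1.26 | 44% / 62% | 0.80 | 1.20 |
| 18/30 | 1.22 / 1.35 | 53% / 66% | about 0.9 | about 1.3 |
| 24/36 | 1.36 / 1.41 | 60% / 69% | 0.96-0.98 | 1.43-1.44 |

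The captured share is in-window years over follow-up years, for example 1.00/2.28 = 44%. The null ratio is the ratio of in-window years, for example 1.00/1.26 = 0.79, against 0.80 simulated. Separate simulation runs differ in the second decimal.

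**Number of cases.** For 12/24 months and equal rates: 350 x 0.01 x 1.00 = 3.5 against 350 x 0.01 x 1.26 = 4.4. Across all scenarios the window holds about 3 to 7 cases per arm, below the 10 per arm needed for the Kaplan-Meier display.

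**Lengthening the window alone is not enough.** Over all disease-free follow-up, equal rates give a crude ratio of 2.28/2.05 = 1.11, because axitinib patients are assumed to stay disease-free, and so under observation, for longer. A true 1.5 reads about 1.65.

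**The case against.** Several points weigh against a stronger version.

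- **Most of the risk period is lost.** A reader might infer this from 28 days against a 5-year study. It holds only if treatment ends at roughly 1 to 1.5 years. At 24 to 36 months the share left out is a minority, and the documents do not give actual durations.
- **More than half the cases are dropped even with equal treatment.** This does not hold in general either: with all patients treated for 24 months, 32% of follow-up is left out.
- **A true excess disappears.** If recurrence, death and dropout are ignored, the 12/24-month scenario gives 0.69 for a null and 1.04 for a true 1.5. The plan's own DFS and dropout assumptions do not allow that simplification, and the distortion shrinks to the figures above.
- **The trial would report a protective effect.** SAP 7.5 plans no formal safety comparison, and the counts are small. With 4 against 5 cases of 350, the ratio is 0.80 with SE(log) = sqrt(1/4 + 1/5 - 2/350) = 0.67, so the 95% interval runs from about 0.2 to 3. The direction is also uncertain: recurrence ends treatment (protocol 6.5.1), which could shorten the placebo window instead.
- **Late cases appear only within DFS.** This is not so. SAP 7.5.1 counts serious TEAEs at any time, including follow-up, and protocol 9.4.1 plans patient listings of all AE data. But the serious row pools every event type, and listings are not a comparison by arm.
- **Protocol 8.5 contradicts 8.2.** They can be read together: 8.5 says what is serious and 8.2 says when it is reported. What is unclear is whether 8.5 applies after 28 days.

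The SAP's open-ended TEAE definition might be thought to cover late cases, but the sentence on by-arm summaries limits them to the observation period. Where the SAP wants a longer period it says so, and it does that only for serious and Grade 5 rows. The table shells are not visible, so the finding is that the visible text describes no such table.

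**Conclusion.** The point holds in a limited form. The planned second-primary summary leaves out a material part of the follow-up in which these cancers are sought, possibly most of it if treatment stops near 1 year. Its crude ratio depends on relative treatment duration. Under the stated assumptions a null reads about 0.80-0.98 and a true 1.5 reads about 1.20-1.44. The loss of follow-up does not depend on the assumed cancer rate or on the arms differing; the sizes quoted do rest on the assumed treatment durations, the rate and exponential times.

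The primary DFS analysis is unaffected. The matter deserves correction because the sponsor named the safety question, already collects the data, and describes no by-arm comparison over the period collected.

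**What to change.** 1. In SAP 7.5.1.2, exempt the carcinogenicity category from the 28-day window. Add a descriptive by-arm table, in the as-treated population, of all second primary malignancies from first dose to end of follow-up, drawn from the AE and SAE pages and from the IRC and investigator DFS assessments.
2. Report incidence per patient-year, or cumulative incidence with recurrence and death as competing events. Crude proportions over full follow-up should not be the only measure. Keep the 28-day count as a secondary row.
3. Reconcile the SAP's open-ended TEAE definition with the 28-day limit in protocol 9.4.1. SAP 7.5.1.2 also refers to 13 categories for the Kaplan-Meier display but lists 14, so state whether carcinogenicity is included.
4. Optionally, clarify in protocol 8.2 how the SAE requirement in 8.5 applies after 28 days. The table does not depend on this, since it can draw on the DFS data.

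Cost: SAP wording and one extra table from data already collected. If 8.2 is clarified to extend reporting, there will be some added SAE reporting during follow-up.

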## **Secondary Endpoints:**

- OS, defined as the time from the date of randomization to the date of death due to any cause. In the absence of confirmation of death, survival time will be censored at the last date the patient is known to be alive. Patients lacking data beyond randomization will have their survival times censored at randomization.
- Type, incidence, severity (graded by the National Cancer Institute [NCI] Common Terminology Criteria for Adverse Events [CTCAE] Version 4.0), timing, seriousness, and relatedness of adverse events, and laboratory abnormalities.

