**6.1.3. Analysis of Time-To-Event Endpoints**

Time-to-event endpoints will be summarized using the Kaplan-Meier method and displayed graphically when appropriate. Median event times and 2-sided 95% CI for each median will be provided based on the Brookmeyer-Crowley method.

Difference in time-to-event endpoints will be tested using a 2-sided stratified or unstratified log-rank test, where applicable. The stratified analysis will be performed as stated in Section 5.4.1.

Cox proportional hazards model will be used to estimate the hazard ratio and its 95% CI.

A parametric model will also be implemented as a sensitivity analysis of DFS.

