**6.2.2. Missing Data in Safety Endpoints**

The percentage of subjects with an adverse event will be calculated using the number of as-treated subjects as the denominator. Therefore, no subjects in the as-treated population are excluded from adverse event displays. The denominator for summary tables for each laboratory parameter will be all subjects in the as-treated population with at least one evaluable cycle for that parameter. Different laboratory parameters may have different denominators, depending on the number of evaluable subjects for each parameter. An evaluable cycle is any cycle with at least one assessment of that parameter. Therefore, subjects with no assessments of a particular laboratory parameter are not included in the analysis of that parameter.

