**7.5.1.2 Treatment Emergent Adverse Events of Special Interest**

The following TEAEs of special interests will be summarized for the as-treated population and by SOC and PT for each categorized treatment group. The list of MedDRA defined SOC and PTs for TEAEs of special interest are provided below and may be updated at the time of database lock based on the MedDRA version in use at the time of reporting and/or any additional safety information available from the Axitinib program that may determine a need to consider additional events of interest. Additionally, for the following special adverse events, Kaplan-Meier methods will be used to display the time to the first occurrence of each of these 13 event categories, if the number of events is  $\geq 10$  events per treatment arm:

| Adverse Events of Special Interest | Search Terms (MedDRA version 20.1)  |
|---|--|
| Cardiac disorders                         | Cardiac disorders – SOC
Cardiac and vascular investigations (excluding enzyme tests)- HLGT  |
| Nervous system disorders                  | Central nervous system vascular disorders- HLGT  |
| Vascular disorders                        | Embolism and thrombosis- HLGT
Pulmonary Embolism PT   |
| Renal vascular disorders                  | Renal vascular and ischaemic conditions (HLT)
Renal failure and impairment (HLT)
Renal hypertension and related conditions (HLT) |

Document: C:\Users\q764206\AppData\Local\Microsoft\Windows\Temporary Internet Files\Content.Outlook\GWW33WM3\ATLAS\_SAPFinal v8.0\_06MAR2018.docx  
 Author: [name] (Updated [name]; [name]; [name], [name]) Version Number: Final 8.0

Version Date: 06MAR2018

Template No: CS\_TP\_BS016 – Revision 2 Reference: CS\_WI\_BS005  
 Effective Date: 01Feb2010

Statistical Analysis Plan

|   |   |
|---|---|
| Haemorrhage                                 | Haemorrhage (excluding lab terms) SMQ (broad and narrow) and Haemorrhage laboratory terms SMQ (broad and narrow)  |
| Hypertension                                | Hypertension SMQ narrow   |
| Proteinuria                                 | MedDRA PTs: Albumin urine present, Proteinuria, Protein urine, and Protein urine present  |
| Thyroid Dysfunction                         | Thyroid dysfunction SMQ broad   |
| Venous Embolic and Thrombotic Events (VTE)  | Embolic and thrombotic events, venous SMQ narrow  |

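### Cheap improvement: adverse events of special interest get only crude between-arm estimates, although time at risk can differ by arm

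*SAP*

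**What the plan says.** SAP 7.5.1 singles out the AESIs: "Selected summaries of subject-incidence of AEs (as defined in Section 7.5.1.2) will include the risk difference", which is "defined as the proportion with the event in the axitinib arm minus the proportion with the event in the placebo treatment arm", and also a risk ratio formed from the same two proportions. Both come with 95% CIs. SAP 6.2.2 fixes the denominator: "The percentage of subjects with an adverse event will be calculated using the number of as-treated subjects as the denominator". The observation period in 7.5.1 runs "from date of the first dose of study treatment until 28 days after the last dose of study drug is administered", so its length follows each subject's time on drug.

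Protocol 5.1 allows up to 3 years of dosing and ends it for recurrence, second malignancy, significant toxicity or withdrawn consent. Table 3 in Protocol 5.3.4.1 requires stopping for related Grade 4 events and for Grade 3 events lasting 2 weeks or more.

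SAP 7.5.1.2 adds Kaplan-Meier curves to "display the time to the first occurrence of each of these 13 event categories, if the number of events is" at least 10 per treatment arm. It names no between-arm estimate to go with them. SAP 6.1.3 says of time-to-event endpoints in general that a "Cox proportional hazards model will be used to estimate the hazard ratio and its 95% CI", but does not say whether time to first AESI is one of those endpoints. SAP 7.4.3 summarises exposure by arm, SAP 7.3.4 plans the cumulative incidence of discontinuation for AEs of interest, and SAP 7.5 plans no formal safety comparisons.

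**The concern.** A crude proportion over a window that closes with treatment mixes two things: how often the harm occurs per unit of time on drug, and how long patients stay on drug. In this trial two forces act on the second. If axitinib delays recurrence, as the design assumes, axitinib patients stay on treatment longer. If it is less well tolerated, they leave sooner. For harms that accrue over time, the crude ratio then also reflects treatment persistence, and the named estimates do not let a reader separate the two.

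Safety is a secondary objective, and the secondary endpoint covers "timing, seriousness, and relatedness of adverse events, and laboratory abnormalities". Patients here have no evident disease and may take the drug for up to 3 years, so harms that build up on treatment matter. The Kaplan-Meier curves do account for time on treatment, but they come without an estimate or interval and are dropped for the rarer categories.

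**Working it through.** The plan gives no safety figure to reproduce and no stop rates by arm, so the check is a range under stated assumptions.

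**Inputs from the plan.** About 700 patients at 1:1, taken as 350 treated per arm. Two-year DFS by category is as in the sample-size table (Protocol 9.1, SAP 3.3). Those rates return the plan's hazard ratios: ln 0.79/ln 0.70 = 0.66, ln 0.61/ln 0.35 = 0.47, ln 0.51/ln 0.33 = 0.61, and weighted 90/1/9% they give 0.654.

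**Stops for DFS events.**
- Placebo 2-year DFS: 0.90×0.70 + 0.01×0.35 + 0.09×0.33 = 0.663, hazard −ln(0.663)/2 = 0.205 per year.
- Axitinib: 0.90×0.79 + 0.01×0.61 + 0.09×0.51 = 0.763, hazard 0.135 per year.

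**Other stops (assumed).** Hazard −ln(1−p) in year 1 and half that afterwards, so the proportion by 18 months is 1 − (1−p)^1.25. This is 6.2% for p = 5%, 12.3% for p = 10% and 24.3% for p = 20%. Only the last is close to the plan's 23% drop-out by 18 months, so placebo is set at p = 20% and axitinib at 20, 30 or 40%.

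**Time on drug.** T = min(stop, 3 years). Mean T is 1.78 years on placebo and 1.94/1.70/1.46 years on axitinib.

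**Crude risk** = 1 − E[exp(−λ(T + 28/365.25))], integrated numerically. Crude risk ratios, with log-scale Wald 95% CIs at the expected counts:

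| True rate ratio (placebo rate per 100 patient-years) | Axitinib stops 20% | 30% | 40% |
|---|---|---|---|
| 2 (1) | 2.15 (0.85 to 5.42) | 1.89 (0.73 to 4.87) | 1.64 (0.62 to 4.34) |
| 1.5 (3) | 1.60 (0.92 to 2.79) | 1.41 (0.80 to 2.50) | 1.23 (0.68 to 2.22) |
| 1 (3) | 1.09 (0.59 to 2.00) | 0.96 (0.51 to 1.80) | 0.83 (0.43 to 1.60) |

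Hand check of the last row: for a rare harm the crude ratio is roughly the true ratio times the ratio of mean windows (28 days = 0.08 year). That gives 2.02/1.86 = 1.09, 1.78/1.86 = 0.96 and 1.54/1.86 = 0.83. For true ratios of 2 and 1.5 the crude ratio equals the true one when axitinib stops are about 25 to 26%. Below that it is too high; above that it is too low.

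**Kaplan-Meier condition.** Ten events in 350 is 2.9%. Display probability = P(Bin(350, placebo risk) ≥ 10) × P(Bin(350, axitinib risk) ≥ 10). In the first row this is 10/9/7%; in the second it is about 99%.

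**Early-onset harm.** Hazard in the first 3 months only, true risks 4.9% and 7.2%, true risk ratio 1.48. The crude ratio is 1.49/1.48/1.46. The patient-year rate ratio is 1.40/1.58/1.80, which is worse.

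**What the added measures return.** If stopping is unrelated to the harm, the patient-year ratio recovers 2.00, 1.50 and 1.00 in the three rows. The true 1-year Kaplan-Meier difference is 0.99 points (1.00% against 1.98%) in the first row and 1.44 points (2.96% against 4.40%) in the second, whatever the stop rates. In simulations with placebo stops of 5%, its standard errors were 0.94 to 1.01 and 1.48 to 1.58 points.

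**Informative stopping.** Take the second row with a strong frailty (gamma, mean 1, variance 1) shared by harm and other stops on axitinib. The rate ratio falls to 1.19/1.11/1.04, and the 1-year difference to 1.02/0.83/0.67 points against 1.35 without stops. Neither measure is fully protected.

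**The case against.** The strongest reply is that the plan is already coherent and descriptive. The risk of an event during treatment as actually taken is a legitimate quantity. No formal safety comparison is planned, timing is shown by the Kaplan-Meier displays, and persistence by the exposure and discontinuation summaries. All of that stands, and it is why the crude estimates should stay. Those separate summaries still do not give a time-based contrast for the events themselves.

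Second, SAP 6.1.3 may already supply a Cox hazard ratio, and the figure shells, which could carry one, are not in the text available. A reader might infer that the SAP omits any time-based safety contrast. The documents do not support that. They show only that 7.5.1 and 7.5.1.2 name none and that the scope of 6.1.3 is unstated.

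Third, sampling error is larger than the distortion for sparse categories. This is correct: every interval in the table contains the true ratio. The added estimates will be just as imprecise there.

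Fourth, second primary malignancy looks like the natural example, but it is a poor one. It is already followed as a DFS component regardless of treatment duration (Protocol 6.4), although only within a composite. The added measures also stop at last dose + 28 days, so late cases would still be missed.

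**Conclusion.** The point holds as an optional improvement, not an error. For AESIs the only between-arm estimates named in SAP 7.5.1 and 7.5.1.2 are crude, and the window behind them depends on time on drug.

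A reader might go further and infer that the crude ratio understates axitinib's harm. The documents do not support a direction. Longer disease-free time on axitinib pushes the ratio up and toxicity stops push it down, and no stop rates by arm are given. With placebo stops of 20%, the crude ratio is within about 10% of the true rate ratio at axitinib stops of 20 or 30%, and about 17 to 18% low at 40%. Larger distortions need other-stop rates of 5 or 10%, well below the plan's drop-out assumption.

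These sizes rest on constant hazards, 350 treated per arm, the plan's DFS rates, and other-stop rates anchored to study drop-out, which is not identical to stopping treatment. Early-onset harms are almost unaffected.

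**What to change.** Keep the crude proportions, risk differences and risk ratios. In SAP 7.5.1.2 add, for each AESI category regardless of event count and labelled as descriptive on-treatment estimates:

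1. As the lead time-based measure, the between-arm difference in Kaplan-Meier cumulative incidence at fixed times (for example 12 weeks and 1 year) with 95% CI.
2. Beside it, for harms that accrue over time, first-event incidence per 100 patient-years by arm and the rate ratio with 95% CI. Time at risk runs from first dose to the earliest of first event, last dose + 28 days, death or data cut-off.
3. One sentence stating whether the Cox rule in SAP 6.1.3 applies to time to first AESI.

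The cost is SAP wording and one more table set from dates already collected, with no effect on patients, sites or the primary analysis. The downsides should be stated with the tables. Patient-year rates assume a roughly constant hazard and mislead for front-loaded events. Stopping for toxicity may be informative. Intervals will be wide for rare events. Neither added measure captures events later than last dose + 28 days, including late second malignancies.
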